physician once and then leave the system), we will include patients who have had 2 or more visits to a CSMG physician in the year prior to the study start date and at least 1 visit during the follow-up year. This will ensure that we have a relatively stable population, which will be critical in calculating the rates outlined in Aim 3 of the study. Prescribed opioid medications include: codeine, dihydrocodeine, tramadol, morphine, hydromorphone, oxymorphone, tapentadol, buprenorphine, methadone, oxycodone, fentanyl, and remifentanil.

Exclusion Criteria: We will exclude individuals less than 18 years of age because the communication comparators include Choosing Wisely and CDC guidelines that do not address the use of opioids in minors. Exclusion criteria also include individuals with treatment for chronic pain during (1) active cancer treatment, (2) palliative care, or (3) end-of-life care. Patients who do not see their primary care provider during the study period will be excluded retroactively from the study.

D3. Study Population. We will conduct this study in the Cedars-Sinai Medical Network, a large, urban, integrated delivery system serving a diverse population. The Cedars-Sinai Medical Network services a large cohort reflective of the national population with regards to insurance coverage as well as chronic pain prevalence and opioid use.⁸⁵ A quality improvement claims-based analysis of patients served by the network found that 30% of individuals at Cedars-Sinai have a chronic pain condition, approximately 22,800 patients in total, consistent with national chronic pain prevalence estimates.⁸¹ Using national chronic pain prevalence data, we estimate that the population for this study is distributed by race and ethnicity as described in Table 1: (RQ3, RQ4)

Table 1. Estimated Race-Ethnicity Distribution of the Study Population for Proposed Study		
	National Chronic Pain Prevalence Data ⁸¹	Estimated Study Population Race-Ethnicity Distribution
Non-Hispanic White	81%	18468
Non-Hispanic Black	8%	1824
Hispanic	5%	1140
Asian	1%	228
Mixed Race	3%	684
Other	3%	684

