E5.c. Power Calculations. Guided by previous work in chronic pain interventions,¹⁴⁰ we calculated sample size using an intracluster correlation coefficient of 0.02, an α level of 0.05, 90% power, and detection of a mean (SD) difference of 0.3 standard deviations on the PROMIS Pain Interference scale. We calculated a sample size of 320 patients per study arm, for a total of 640 patients. To compensate for predicted loss to follow-up, multiple variables in the final multi-level models, as well as sub-group analyses, we inflated the sample size by 50% to 960. Since we will be examining the effect of the interventions on a variety of sub-groups within the study sample, such as diagnoses of mental health conditions, race, ethnicity, gender, and chronic pain diagnosis, we will be adequately powered to detect meaningful differences. In our original proposal, we calculated a sample size of 320 patients per study arm for a total of 640 patients. To compensate for predicted loss to follow-up and non-response we had inflated the recruitment target size by 50% to 960. Under the current modification – and given the absence of changes to the assessment schedule, the estimated intracluster correlation coefficient, and the expected mean difference - the sample size required to adequately power the analysis remains unchanged. We believe the recruitment target will also remain consistent, and potentially even fall due to the ability of study staff to call passively enrolled patients and remind them to respond to assessments. We therefore anticipate being adequately powered to detect meaningful differences between the two arms.

E6 Heterogeneity of Treatment Effect (HT-1, HT-3, HT-4)

After reviewing the literature and consulting with our patient partners, we identified specific subgroups we plan to analyze to identify whether there is a heterogeneity of the treatment effects. Below we detail our planned sub-group analyses, our hypotheses, and our plans for statistical analysis for each subgroup. In order to address the problem of multiplicity, a Bonferroni correction will apply to all analyses.

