▪ **Race/Ethnicity. Hypothesis:** Previous literature finds that providers might be less likely to engage in shared decision-making with non-White patients.²⁴ It is plausible that the interventions, particularly the PEATs, may be less effective for non-White patients as a result of provider-level factors. Lower satisfaction with communication should result in lower improvements in HRQOL. This analysis can inform future development of CDS or PEATs. **Outcomes analyzed:** Communication satisfaction scores as measured by CG-CAHPS and HRQOL scores as measured by the PROMIS Physical Function, PROMIS Depression, and PROMIS Pain Interference Survey. **Statistical analysis plan:** Statistical interaction in regression models

▪ **Mental Health Diagnosis of Depression, Anxiety Disorder, Prior Substance Abuse Disorder or PTSD. Hypothesis:** Patients with diagnoses of depression, anxiety disorder, Substance Abuse Disorder, or PTSD should see improved

communication scores as measured by CG-CAHPS in the CDS arm because one alert specifically targets these conditions and prompts physicians to discuss risks and benefits of opioids for these patients, who are at higher risk of opioid abuse disorder. *Outcomes analyzed:* CG-CAHPS scores, high-risk opioid prescriptions at the end of the intervention. *Statistical analysis plan:* Statistical interaction in the regression models.

- **Gender. Hypothesis:** Prior studies have found that women are more likely to encounter providers who do not believe their pain is real or who believe that they are exaggerating their pain.⁵³ We believe that female patients in the PEAT arm will see greater effect on their HRQOL as a result of shifting the conversation from pain alone to other important Patient-Reported Outcomes such as fatigue, appetite, mood. *Outcomes analyzed:* HRQOL scores. *Statistical analysis plan:* Statistical interaction in the regression models.

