b. Statistical Methods to Handle Missing Data and Sensitivity Analyses. If the data is not missing at random, we will use multiple imputation techniques to impute missing data for respondents (MD-2). We plan on using the *mi impute mvn* command in Stata and will generate 20 datasets compatible with the regressions planned for the final analyses. To insure that the imputation has proceeded as expected, we will visually inspect parameters from successive iterations of the model to determine if they have reached a stationary distribution. We will conduct sensitivity analyses with the dataset that includes imputed data as well as with a dataset that does not include imputed data to determine the effect of the multiple imputation and plan on reporting both results. These precautions will serve to identify autocorrelation in the imputed data and allow for proper maintenance of uncertainty in imputed values (MD-3).

c. Reporting Reasons for Dropout and Missing Data. We will drop data from patients who do not have any visits with their PCP during the intervention period or are lost to follow-up, but will compare descriptive statistics for these patients to patients with at least one visit to their PCP for sensitivity analysis (MD-4, MD-5).

E9. Project Milestones and Timeline.

During the first 3-6 months of the study project, we will train the project staff, refine the study protocol, develop the data dictionaries, and obtain IRB approval. We will hold monthly meetings with our patient partners to finalize the study design and discuss issues related to IRB approval. In Year 1, Q4, we will passively enroll eligible patients in the two study arms. In the 4 weeks before the intervention period, we will send baseline questionnaires via REDCap. In Year 2, we will begin the intervention. We will conduct weekly reports from our EHR data warehouse to determine enrolled patient visits. Enrolled patients will be sent CG-CAHPS survey one day after each primary care visit. Enrolled patients will also receive the PROMIS questionnaires once a month. We will perform monthly checks to assess the completeness of data to minimize missing data and will complete one set of interim data analyses in Year 2 to assess whether there are any issues with missing data. Full data analysis will

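### Adequate power for subgroups is asserted without a calculation to support it, and it is unclear whether the Bonferroni correction covers the two outcomes labelled primary

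*Combined protocol and SAP*

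**What the plan says.** **Subgroups.** E5.c gives one calculation: intracluster correlation 0.02, α 0.05, 90% power, a 0.3 SD difference between arms on PROMIS Pain Interference, 320 patients per arm (640), raised to 960. The reasons for the increase are loss to follow-up, "multiple variables in the final multi-level models, as well as sub-group analyses, we inflated the sample size by 50% to 960". It then states that for subgroups "such as diagnoses of mental health conditions, race, ethnicity, gender, and chronic pain diagnosis, we will be adequately powered to detect meaningful differences". E6 names race/ethnicity, mental health diagnosis and gender, each tested by "Statistical interaction in the regression models" or near-identical wording, and adds that "a Bonferroni correction will apply to all analyses".

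**Data for those tests.** E9 says "Enrolled patients will also receive the PROMIS questionnaires once a month" and "Enrolled patients will be sent CG-CAHPS survey one day after each primary care visit". D2 requires "at least 1 visit during the follow-up year". E5.b plans growth models and lists baseline HRQOL as a potential covariate. Model 2, for CG-CAHPS, lists no baseline CG-CAHPS score.

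**Primary outcomes.** E5.b labels both Model 1 (pain interference) and Model 2 (CG-CAHPS) as primary, and the Communication Questionnaire item under Outcome Measurement (E6.d) also calls CG-CAHPS primary. Item 7 of the PRECIS list names pain interference as the main outcome.

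**The concern.** A sample size for a main effect does not carry over to an interaction, whose standard error is at least twice that of the main effect and grows as the split becomes uneven. The reason E5.c offers for adequate subgroup power is that subgroups will be examined, together with an inflation shared with loss to follow-up and model covariates.

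Heterogeneity is part of Aim 2. Without a stated detectable difference, a non-significant race or gender interaction could be read as evidence that the strategies work equally well for everyone.

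The multiplicity question affects the main conclusion. With two outcomes labelled primary, either the chance of a false claim or the stated power depends on a Bonferroni family that the plan does not define.

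**Working it through.** **Inputs from the plan.** N = 640 or 960 (E5.c); about 1,200 full responders (30% of 4,000, E4.d); women 62% (D3); non-Hispanic White 81% (D3, Table 1), so 19% otherwise.

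**Assumptions of this review.** Two-sided tests, equal arms, complete data, and an interaction of 0.3 SD. The plan gives 0.3 SD only for the main effect and states no interaction size.

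**The plan's own figure.** Without clustering, 2 × (1.960 + 1.282)² / 0.3² = 233.5 per arm, and 320 / 233.5 = 1.37. So 320 fits one score per patient with a design effect of 1.37. The plan states neither the cluster size nor the number of scores, so this is an inference.

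**Formulas, in SD units.** SE = √[4v / (N p(1−p))]. Power = Φ(0.3/SE − z), with z = 1.960 at α 0.05 and 2.807 at 0.005. Here p is the subgroup share and v the variance of the patient summary relative to one score. No cluster penalty is applied, because these modifiers vary within a physician's patients.

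**1. One score, v = 1**

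| | SE, N=640 / 960 | Power at 0.05 | Power at 0.005 |
|---|---|---|---|
| Gender | 0.163 / 0.133 | 45% / 62% | 17% / 29% |
| Race | 0.201 / 0.165 | 32% / 45% | 9% / 16% |

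The 0.005 column is 0.05/10 on one count of E6: race × 4 outcomes, mental health × 3 (counting high-risk prescribing as two), gender × 3. The plan gives no count. At N = 1,200 and α 0.05, power is 71% for gender and 53% for race. Applying the 1.37 penalty lowers the 0.05 figures to 35% / 49% and 25% / 34%.

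**2. PROMIS, mean of 12 monthly scores, baseline-adjusted.** With an assumed equal correlation r, v = (1 + 11r)/12 − r². This is 0.268 at r = 0.3, peaks at 0.293 near r = 0.46 and falls to 0.177 at r = 0.8. At N = 960:

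- Gender: 0.05 gives 98.6% or more; 0.005 gives 91-99%.
- Race: 0.05 gives 92-99%; 0.005 gives 71-94%.

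At N = 640 and 0.005, gender is 72-94% and race 48-77%.

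**3. What lowers these figures.** If the target is a linear slope reaching 0.3 SD at month 12, v = (1−r)/Σ(t−t̄)² with 13 points on 0 to 1. The sum is 1.264, so v = 0.158-0.554. At N = 960 and 0.005, gender runs from 59% to over 99% and race from 36% to 96%. This allows no between-patient slope variance; adding it lowers power further. Correlation that decays with time also costs power: AR(1) at 0.9 gives v = 0.397, hence 78% and 54%. Missing months act in the same direction.

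**4. CG-CAHPS.** With an assumed 1-3 visit scores, no baseline and r 0.3-0.8, v = (1 + (m−1)r)/m runs from 1 (m = 1) to 0.53 (m = 3, r = 0.3). For race at N = 960, power is 45-70% at 0.05 and 16-38% at 0.005. Using 0.3 SD for this outcome is a further assumption.

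**5. Detectable interaction, one score, N = 960, 90% power.** SE × (z + 1.282): 0.43 SD (gender) and 0.53 SD (race) at 0.05; 0.54 and 0.67 SD at 0.005.

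**6. Two primaries.** Both unadjusted: 1 − 0.95² = 9.75% if independent, and 10% at most. Both at 0.025, taking the stated 90% as exact: Φ(1.960 + 1.282 − 2.241) = Φ(1.00) = 84%. Restoring 90% takes 320 × (2.241 + 1.282)² / (1.960 + 1.282)² ≈ 378 per arm.

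**The case against.** The strongest reply is that the analysis is longitudinal. Monthly PROMIS scores with baseline adjustment can bring gender, and often race, to ample power, as step 2 shows. That stands. A reader might infer from step 1 that the trial is underpowered for its subgroups, but the documents do not support this: the one-score basis is inferred and the 0.3 SD interaction is assumed. A larger interaction would be easier to detect; at 0.6 SD with the 1.37 penalty, power over N = 640 to 960 is 88-97% for gender and 72-88% for race. The reply does not rescue the sentence in E5.c, however, because the plan gives none of the inputs on which the gain depends.

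A reader might also infer that E5.c contradicts itself, because it later says "To compensate for predicted loss to follow-up and non-response we had inflated the recruitment target size by 50% to 960" without mentioning subgroups. That sentence describes the original proposal, so the difference is not an error, and it does not show that nothing is left for subgroups.

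On CG-CAHPS, one visit is an eligibility minimum and not the expected number. The network already collects the survey, so earlier scores may exist, and the covariate lists are only potential. This is why 1-3 scores is marked as an assumption.

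On multiplicity, the Bonferroni sentence sits in the subgroup section and may be meant only for it; PRECIS item 7 and the sizing both point to one main outcome. The 10% figure applies only if success on either outcome would support a claim, which the plan does not say. The ambiguity remains on either reading.

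**Conclusion.** The general claim of adequate subgroup power is unsupported. Depending on choices the plan leaves open (outcome, number of scores, correlation, contrast, adjusted α), power for a 0.3 SD interaction at N = 960 ranges from 16% (race, one score, 0.005) to over 99% (gender, 12 baseline-adjusted PROMIS scores, 0.05). PROMIS mean levels may well be adequately powered. CG-CAHPS, an E6 outcome for race and mental health, is the weaker case. Power for the binary prescribing outcomes was not assessed, and the documents give no share for the mental health subgroup.

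The multiplicity gap holds on either reading: family-wise error up to about 10% if the primaries are unadjusted and either suffices, or about 84% power in place of 90% if α is divided between them. Both parts should be fixed. No figure printed in the plan is shown to be wrong.

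**What to change.** **Subgroups (E5.c, E6).** Replace the sentence on subgroup power with the detectable interaction for each outcome, stating analysed N, number of scores, within-patient correlation, contrast (mean level, month 12 or slope) and Bonferroni-adjusted α. The one-score values in step 5 can serve as the conservative case. Give CG-CAHPS its own target and expected number of scores. Report E6 interactions as estimates with confidence intervals, and say that non-significance will not be read as absence of heterogeneity.

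**Primaries (E5.b, E5.c).** Either name pain interference the single primary at 0.05, which matches PRECIS item 7 and the sizing, with CG-CAHPS as key secondary; or test both at 0.025 and restate power.

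**Bonferroni family (E6).** List its tests. Say whether the primaries belong, and whether the further moderators in E5.b do (age, education level, pain diagnosis, physician years of practice and gender). Pain diagnosis is named in the E5.c power claim but has no entry in E6.

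**Cost.** Wording only for the subgroup text and for naming one primary. The subgroup power statement becomes less favourable. Making CG-CAHPS secondary departs from the patient partner's suggestion, recorded in Table 4, that communication be a primary outcome. Splitting α keeps both, at about 6 points of pain-interference power at 320 per arm, or 378 analysed per arm to keep 90%.

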Question: Which communication strategy used during the clinical encounter is more effective in reducing pain interference over time for patients with chronic pain who were taking opioids at baseline?

Dependent variable: Pain interference as measured by PROMIS Pain Interference Score (T-Score, Continuous)

Independent variable: Comparator received, CDS vs. PEAT (Dichotomous)

Potential Covariates: Age, gender, race, ethnicity, mental health comorbidities, chronic pain diagnosis, use of other pain medications (neuropathic pain medications, NSAIDS, antidepressants), benzodiazepine use, number of office visits during intervention period, baseline HRQOL, encounter month, physician years of practice, physician gender, employment, SES.

Moderator Analyses: We will use statistical interactions examining the moderating effects of patient age, race, ethnicity, mental health comorbidities, chronic pain diagnosis, physician years of practice and physician gender on the relationship between comparator and pain interference.

Mediation Analyses: We will test whether confidence in decision and satisfaction with communication as measured by COMRADE Scores mediates the relationship between the comparator used and the pain interference outcomes.

Primary Outcome: Model 2: Hierarchical Linear Model (Longitudinal Analysis)

Question: Which communication strategy used during the clinical encounter is more effective in improving how satisfied patients feel over time after communicating with their physician about chronic pain treatment risks and benefits?

Dependent variable: CG-CAHPS

Independent variable: Comparator received, CDS vs. PEAT (Dichotomous)

Potential Covariates: Age, gender, race, ethnicity, educational level, mental health comorbidities, chronic pain diagnosis, use of other prescribed pain medications (neuropathic pain medications, NSAIDS, antidepressants) benzodiazepine use, number of office visits during intervention period, baseline HRQOL, encounter month, physician years of practice, physician gender, employment, SES.

Subgroup Analyses: We will use statistical interactions examining the moderating effects of patient age, race, ethnicity, education level, mental health comorbidities, chronic pain diagnosis; and physician years of practice and gender on the relationship between comparator and pain interference.

Secondary Outcome: Model 3: Hierarchical Linear Model

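### Holm's step-down over the same tests would control the same family-wise error as the planned Bonferroni correction, never reject less, and gain 4 to 5 points of power per primary outcome if both effects are real

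*Combined protocol and SAP*

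**What the plan says.** The only multiplicity rule stands at the end of the introduction to E6, Heterogeneity of Treatment Effect: "In order to address the problem of multiplicity, a Bonferroni correction will apply to all analyses". It follows directly on "Below we detail our planned sub-group analyses, our hypotheses, and our plans for statistical analysis for each subgroup". No family of tests, number of tests or adjusted significance level is given.

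E5.b labels two models as primary: Model 1 (PROMIS Pain Interference) and Model 2 (CG-CAHPS). Models 3 to 5 are secondary. Models 1 and 2 also list moderator interactions, seven and eight of them. E6 lists three subgroup factors, each tested by interaction on several outcomes.

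The sample size in E5.c uses "an α level of 0.05, 90% power", "detection of a mean (SD) difference of 0.3 standard deviations on the PROMIS Pain Interference scale" and "an intracluster correlation coefficient of 0.02". The result is "We calculated a sample size of 320 patients per study arm, for a total of 640 patients", and then "we inflated the sample size by 50% to 960". The significance level there is not divided by any number of tests, and only pain interference is powered.

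**The concern.** Single-step Bonferroni holds every test in a family of k to 0.05/k, whatever the other tests show. Holm tests the smallest p-value at 0.05/k. If that is rejected, it tests the next at 0.05/(k−1), and so on, stopping at the first failure. Each threshold is at least as lenient as Bonferroni's, so everything Bonferroni rejects Holm also rejects. The family-wise error bound is the same and holds under any dependence.

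What is at stake is mainly the second primary outcome. The conceptual model in E2 has communication strategies changing communication, which in turn changes patient outcomes. Section F (Threats to Internal Validity) uses CG-CAHPS to judge whether a change in HRQOL came from the intervention. Establishing both primary effects therefore comes close to the trial's scientific aim, and that is where single-step Bonferroni loses most.

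**Working it through.** **The plan's own figure.** For 0.3 SD, two-sided 0.05 (sidedness is not stated, so assumed) and 90% power: n = 2 × (1.960 + 1.2816)² / 0.3² = 233.5, so 234 per arm before clustering. The stated 320 implies a design effect of 320/234 = 1.368. With ICC 0.02 this means 1 + 0.368/0.02 = 19.4 patients per cluster. The cluster size is not stated, and 640 patients over the 80 PCPs in E4.d would give 8. I take the planned 90% as given and vary it below.

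**Two primaries, both effects real.** The expected z-statistic for each is 1.960 + 1.2816 = 3.2415.

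- Power at 0.05: 0.900.
- Power at 0.025 (critical value 2.2414): Φ(3.2415 − 2.2414) = 0.8414.
- Holm, per outcome, independent tests: 0.8414 + (0.9000 − 0.8414) × 0.8414 = 0.8907.
- Both established, Bonferroni: 0.8414² = 0.708.
- Both established, Holm: 0.9000² − 0.0586² = 0.807.
- At least one rejected, either method: 1 − (1 − 0.8414)² = 0.975. Holm's first step is the Bonferroni step, so this is identical.

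The correlated case comes from the bivariate normal distribution:

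| Correlation | Per outcome, Bonferroni | Per outcome, Holm | Both, Bonferroni | Both, Holm |
|---|---|---|---|---|
| 0 | 84.1% | 89.1% | 70.8% | 80.7% |
| 0.3 | 84.1% | 88.6% | 72.8% | 81.7% |
| 0.5 | 84.1% | 88.2% | 74.5% | 82.6% |

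**Two primaries, one effect real.** Under independence, Holm's power for the real effect is 0.8414 + 0.0586 × 0.025 = 0.843, a gain of about 0.2 points. The chance of falsely rejecting the null outcome rises from 2.5% to 0.025 + 0.8414 × 0.025 = 4.6%, still within 5%.

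**Sensitivity to starting power (independent tests, both real, same power for each).**

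- With 8 patients per PCP, 320 per arm gives 94.5% at 0.05 and 90.5% at 0.025. The gain per outcome is (0.9445 − 0.9054) × 0.9054 = 3.5 points.
- With all 480 per arm analysed at the implied design effect, the figures are 97.8% and 95.8%. The gain is (0.978 − 0.9584) × 0.9584 = 1.9 points.

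**E6 interactions.** Race/ethnicity has four outcomes, mental health two (three if both high-risk prescribing measures count) and gender three, so 9 or 10 tests. I assume subgroups of equal size and an interaction as large as the main effect. The interaction then has about twice the standard error of the main effect, so the expected z is 3.2415/2 = 1.62. Power is 37% at 0.05 and 12.5% at 0.05/9. Simulation with nine tests at correlation 0.3 gives average power, Bonferroni against Holm:

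- all nine real: 12.5% against 14.5%;
- three real: 12.5% against 12.9%;
- one real: 12.3% against 12.4%.

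Simulated family-wise error in the two-test runs stayed within 5% for both methods.

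**The case against.** The strongest reply is that Bonferroni is valid and pre-specified, and that preferring it contradicts nothing in the plan. That stands: the point concerns a better choice, not a mistake.

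The second reply concerns scope. The sentence sits in the subgroup section. If it governs only subgroup tests, the primary-outcome figures do not apply and what is left is a gain of 0.1 to 2 points. This also stands, because the words "In order to address the problem of multiplicity, a Bonferroni correction will apply to all analyses" and their placement point in different directions.

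A reader might infer more than the documents support:

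- *Holm has strictly more power.* Not for the chance of at least one rejection, which is identical.
- *The subgroup tests gain several points.* A family of ten with five real effects gives average power of 66.8% against 70.7% only if each interaction has 90% power at 0.05. E5.c gives that power to a main effect, not to any interaction.
- *The change is free.* Bonferroni has simple matching simultaneous intervals and Holm does not.
- *Two Holm families, the primaries and the E6 interactions, each at 0.05, would give the same protection.* They would not. Models 3 to 5 and the moderator tests in Models 1 and 2 would lose the correction that the present wording gives them.

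**Conclusion.** The point holds as an optional improvement. Over any fixed family, Holm gives the same family-wise error control and never rejects less than Bonferroni.

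The gain of 4 to 5 points per primary outcome, and of 8 to 10 points for establishing both, needs three conditions: the rule covers Models 1 and 2 as a family of two, both effects are real, and each has 90% power at two-sided 0.05. The plan states none of these. The gain shrinks if starting power is higher and nearly vanishes if only one effect is real.

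Holm does not recover the planned 90%. If Bonferroni covers both primaries, 90% power at 0.025 needs 276 × 320/234 = 377.4, so 378 per arm, at the implied design effect. That the sample size uses an undivided 0.05, and that the families are not listed, are separate matters which Holm does not settle.

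**What to change.** Replace the E6 sentence with: *Holm's step-down procedure will be applied in place of single-step Bonferroni, over the same sets of tests to which the Bonferroni correction would have applied.* This keeps every analysis under the correction it now has. Holm needs those sets listed in advance just as Bonferroni does, so the sponsor should name them when making the change, before outcomes are compared by arm.

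The cost is one sentence and no patients. Because Holm lacks equally simple matching simultaneous intervals, report Bonferroni-adjusted intervals, or clearly labelled unadjusted ones, beside the Holm-adjusted p-values. Note that an unadjusted interval can exclude zero when the Holm test does not reject, and a Bonferroni interval can include zero when it does.
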